## 6.3.2.6. Virologic effectiveness

Among suppressed (VL< 50 copies/mL) at initiation:

Maintaining virologic suppression: Among PWH who were suppressed (VL <50 copies/mL) at baseline, the number and proportion who remain suppressed (VL <50 copies/mL) throughout all of follow-up will be reported, as well as the number and proportion who are suppressed (VL <50 copies/mL) at last follow-up. Proportion of individuals with VL <50 copies/mL during the first 6 months, and at 6, 12, 24, 36, 48, and 60 months following initiation of CAB+RPV LA regimen will be described.

Confirmed virologic failure: Confirmed virologic failure will be defined as 2 consecutive follow-up VLs ≥200 copies/mL OR 1 follow-up VL ≥200 copies/mL + discontinuation within 4 months of VL ≥200 copies/mL. The number and proportion of PWH with confirmed virologic failure will be reported as well as the time to virologic failure (months). Proportion of individuals with confirmed virologic failure (CVF) during the first 6 months, and at 6, 12, 24, 36, 48 and 60 months following initiation of CAB+RPV LA regimen will be described.

Among viremic ( $VL \ge 50$  copies/mL) at initiation:

Achieving virologic suppression: Among PWH who were viremic ( $VL \ge 50$  copies/mL) at baseline, the number and proportion who achieve a VL < 50 copies/mL at any point during follow-up will be reported, as well as the number and proportion who achieve a VL < 50 copies/mL at last follow-up. Proportion of individuals with VL < 50 copies/mL during the first 6 months, and at 6, 12, 24, 36, 48 and 60 months following initiation of CAB+RPV LA regimen will be described.

Non-response: VL ≥50 copies/mL after 6 and 12 months following initiation of CAB+RPV LA regimen and also no VL of <50 copies/mL during follow up will be described.

Confirmed virologic failure defined as:

- Suppressed to <50 copies/mL followed by either 2 VLs ≥200 copies/mL or
  1 VL ≥200 copies/mL and discontinuation within 4 months for every other month
  regimen; and discontinuation within 2 months for monthly regimen. Proportion of
  individuals with confirmed virologic failure (CVF) during the first 6 months, and at
  6, 12, 24, 36, 48 and 60 months following initiation of CAB+RPV LA regimen will
  be described.

- FDA's ask: Suppressed to <50 copies/mL followed by either 2 VLs ≥400 copies/mL

Protocol Final ViiV Healthcare 216990 - Amendment 2

or 1 VL ≥400 copies/mL and discontinuation within 4 months for every other month regimen; and discontinuation within 2 months for monthly regimen. Proportion of individuals with confirmed virologic failure (CVF) during the first 6 months, and at 6, 12, 24, 36, 48 and 60 months following initiation of CAB+RPV LA regimen will be described.

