#### **Primary Objectives:**

- 1. To describe baseline demographics, clinical characteristics and patterns of use among PWH receiving CAB+RPV LA at Year 3, Year 4, and Year 5 of availability
- 2. To assess the persistence, adherence and discontinuation among PWH receiving CAB+RPV LA at Year 3, Year 4, and Year 5 of availability
- 3. To assess virologic effectiveness among PWH receiving CAB+RPV LA at Year 3, Year 4, and Year 5 of availability
- 4. To assess factors associated with confirmed virologic failure among PWH receiving CAB+RPV LA regimen at Year 3, Year 4, and Year 5 of availability

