#### 6.3.3.2. Effect modifiers

Participant characteristics, adherence, persistence, discontinuation and virologic effectiveness will be compared in subgroups stratified by viral load at initiation (<50 copies/mL vs. ≥50), BMI (≥30 kg/m² vs. <30 kg/m²), age (18-50, 50-64, ≥65 years), race/ethnicity (non-Hispanic Black, Hispanic, non-Hispanic White), and sex/race (non-Hispanic Black men, Hispanic men, Black women) strata at initiation of CAB+RPV LA.

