# 6.7. \*Data analysis

# 6.7.1. Primary Analysis

## 6.7.1.1. Main Analytical approach

Baseline characteristics and outcomes will be described using counts and absolute and relative frequencies for categorical variables and medians with interquartile ranges (IQR) for continuous variables. For outcomes assessed at any point during follow-up, incidence rates will be estimated using unadjusted Poisson regression, accounting for person-time since index (i.e., first CAB+RPV LA injection).

Analyses will be stratified by viral load (<50 copies/mL vs. ≥50 copies/mL), BMI (<30 kg/m² vs. ≥30 kg/m²), age (18-50, 50-64, ≥65 years), race/ethnicity (non-Hispanic Black, Hispanic, non-Hispanic White), and sex/race (non-Hispanic Black men, Hispanic men, Black women) strata at first CAB+RPV LA injections as sample size allows to assess characteristics, adherence, persistence, discontinuation and virologic effectiveness. Other demographic and clinical variables may also be considered for stratification, if relevant.

Factors including age, sex, race, geographic region, BMI, IDU, CD4 count, any comorbidities associated with confirmed virologic failure will be assessed using multiple logistic regression.

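### Confirmed virologic failure is defined differently for suppressed and viremic starters, without explanation, although the two strata are to be compared on it

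*Protocol*

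**What the plan says.** All definitions are in Protocol section 6.3.2.6.

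- **Suppressed at initiation (VL <50).** "Confirmed virologic failure will be defined as 2 consecutive follow-up VLs ≥200 copies/mL OR 1 follow-up VL ≥200 copies/mL + discontinuation within 4 months". The 4 months run from the elevated VL, and dosing schedule plays no part.
- **Viremic at initiation (VL ≥50), threshold 200.** "Suppressed to <50 copies/mL followed by either 2 VLs ≥200 copies/mL or" one such VL with discontinuation. The window is 4 months for every-other-month dosing, "and discontinuation within 2 months for monthly regimen".
- **Viremic at initiation, threshold 400.** The same structure at the higher threshold, labelled as a request from the regulator: two VLs, again without *consecutive*, "or 1 VL ≥400 copies/mL and discontinuation within 4 months for every other month regimen; and discontinuation within 2 months for monthly regimen".

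Section 6.3.3.2 then states that "virologic effectiveness will be compared in subgroups stratified by viral load at initiation (<50 copies/mL vs. ≥50" copies/mL). Primary objective 4 (section 5) is "To assess factors associated with confirmed virologic failure among PWH receiving CAB+RPV LA regimen", and section 6.7.1.1 describes the model: "Factors including age, sex, race, geographic region, BMI, IDU, CD4 count, any comorbidities associated with confirmed virologic failure will be assessed using multiple logistic regression". Neither place restricts that model to a VL stratum, and baseline VL is not among the factors named.

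**The concern.** CVF carries one name but depends on two rules, and baseline VL decides which applies. The prior-suppression requirement for viremic starters has an obvious purpose: someone who never suppressed cannot rebound, and the plan counts that person under non-response. The other two differences have no such purpose in the text. Nothing explains why a confirming VL must be consecutive in one stratum only, or why the monthly window is halved in one stratum only.

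At stake is what the VL-subgroup contrast measures. If the same VL and discontinuation history counts as failure in one stratum and not in the other, part of any observed difference comes from the definition. The factor analysis for primary objective 4 would share the problem if it spans both strata. CVF also selects the people described under secondary objectives 5 and 6 and starts the 4-week testing window in section 6.3.2.7, so the flag matters beyond the proportion itself.

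**Working it through.** The protocol gives no figure that bears on this point, so the main check is a comparison of the rules.

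**1. The rules side by side (threshold 200)**

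| Element | Suppressed starters | Viremic starters |
|---|---|---|
| Prior condition | VL <50 at baseline | suppression to <50 during follow-up |
| Two-VL route | two consecutive VLs | two VLs; *consecutive* absent |
| One-VL route, every other month | discontinuation within 4 months | discontinuation within 4 months |
| One-VL route, monthly | discontinuation within 4 months | discontinuation within 2 months |

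**2. Histories that are classified differently**

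- *Monthly window.* At 30.4375 days per month, 2 months is 2 × 30.4375 = 60.9 days and 4 months is 4 × 30.4375 = 121.75 days. Take a monthly user with a single VL ≥200 who discontinues 90 days later. This person is a CVF if suppressed at the start and not a CVF if viremic at the start. No interpretation is needed, because both windows are written out.
- *Two-VL route.* Take VLs of 220, <50, <50 and 210 after suppression, with no discontinuation. A suppressed starter is not a CVF. A viremic starter is a CVF if the text is read literally, and is not if the two VLs are understood as successive results.

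**3. Direction**

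On the literal reading, omitting *consecutive* can only add failures among viremic starters. The shorter monthly window can only remove them. For monthly users the two effects oppose each other. The documents give neither the share on monthly dosing nor the frequency of VL testing, so the net sign for the stratum is unknown.

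**4. Illustration of the two-VL route only**

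Assumptions that are not in the documents: *k* independent VLs after suppression, each with probability *p* of being ≥200.

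- At least two of *k*: 1 − (1−p)^k − k·p·(1−p)^(k−1).
- At least two adjacent: 1 − Σ_j C(k−j+1, j)·p^j·(1−p)^(k−j).

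For k = 6 and p = 0.05:

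- At least two: 1 − 0.7351 − 0.2321 = 0.0328.
- At least two adjacent: 1 − (0.7351 + 0.2321 + 0.0204 + 0.0004) = 0.0120.

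| k | p = 0.02 | p = 0.05 | p = 0.10 |
|---|---|---|---|
| 2 | 0.04% vs 0.04% | 0.25% vs 0.25% | 1.0% vs 1.0% |
| 4 | 0.23% vs 0.12% | 1.40% vs 0.73% | 5.23% vs 2.80% |
| 6 | 0.57% vs 0.20% | 3.28% vs 1.20% | 11.4% vs 4.6% |

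Each cell shows any two against two adjacent. The ratio is 1 with two tests and about 1.9 to 2.9 with four to six. Real VLs are correlated within a person, sustained failure meets both rules, and the one-VL route may already capture some of the same people. The table shows that the wording can matter, not by how much it does here.

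**5. People affected**

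Section 6.5 reports 1,578 suppressed starters, 229 viremic starters and 36 without a VL, total 1,843, from the two-year data. The viremic rule therefore applied to 229/1,843 = 12.4% of that cohort. Later cuts are expected to be larger.

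**The case against.** Five arguments can be made for the plan.

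- **The protocol never says *any* two VLs.** Under the label *confirmed*, suppression followed by two elevated results is naturally read as a sequence in which the second result confirms the first. This stands: the omission may be a slip. But *consecutive* appears in one definition and is missing from two in the same section, so someone coding from the text could reasonably code them differently. The window difference does not depend on this reading.
- **A rationale is given.** The summary of changes for Amendment 2 ties the viremic definition to treatment guidelines, the sponsor's own observational definitions and the regulator's proposed assessments for a registrational study. That supports having a viremic definition. It does not explain either difference.
- **Pooling is not stated.** A reader might infer that one regression mixes both outcomes. The documents do not establish this. Section 6.7.1.1 stratifies analyses by VL in the paragraph before the model and does not name baseline VL as a factor, which also fits separate models. Pooling is possible because no restriction is written, but it remains an inference.
- **The analyses are descriptive.** Section 6.9.1 says so, and no test between VL strata is specified. This limits the consequence. Even so, section 6.3.3.2 says the subgroups will be compared, and proportions shown together under one label will be read as comparable.
- **The strata differ by design in any case.** Prior suppression is required of viremic starters and will remain so. That is a stated, understandable difference, and it does not justify two unexplained ones.

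**Conclusion.** The inconsistency is real and is in the current text. CVF is defined differently by baseline VL stratum in two respects beyond the prior-suppression requirement, neither is explained, and the strata are to be compared. The monthly-window difference is explicit. The *consecutive* difference rests on a literal reading of an omitted word.

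A reader might go further and conclude that the plan inflates failure among viremic starters by some multiple. The documents do not support that. The two differences oppose each other for monthly users, and the ratios in the working depend on an assumed per-test probability, assumed numbers of tests and independence. No size or direction can be claimed for the net effect. The conclusion is that the contrast is partly definitional by an unknown amount, which a small correction would remove. It should be corrected before the next analysis, but it does not invalidate the study.

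**What to change.** Reconcile the definitions in section 6.3.2.6:

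- Write two consecutive VLs in the viremic ≥200 definition.
- Use the same discontinuation window for a given dosing schedule in both strata. The sponsor should choose the window; this review takes no position on which is right.
- Apply this definition in the VL-subgroup comparison and in primary objective 4, with prior suppression as the only stated difference for viremic starters.
- Keep the ≥400 definition as a separate supplementary endpoint. The regulator's request is not reproduced in the protocol, so check against it whether consecutive VLs are required before changing that wording.

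The cost is a text change and re-derivation of one flag from data already held. CVF counts may change from any earlier tables that used the current wording; if the sponsor settles on a different window for monthly users in the suppressed stratum, counts there may change too. The protocol does not show which wording the Year 3 tables used: their final version was planned for August 2024, and the viremic CVF definition came with Amendment 2 on 05 September 2024. Year 5 preliminary tables are planned for July 2026.

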## **Study Period:**

- o Year 3:
  - Period of eligibility: 21JAN2021-31DEC2023
  - Period of observation: 21JAN2021-29FEB2024
- O Year 4:
  - Period of eligibility: 21JAN2021-31DEC2024
  - Period of observation: 21JAN2021-28FEB2025
- o Year 5:
  - Period of eligibility: 21JAN2021-31DEC2025
  - Period of observation: 21JAN2021-28FEB2026

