#### **Censoring criteria:**

- Discontinuation of regimen of interest
- Death
- Loss to follow-up (12 months after last clinical contact)
- Study end (end of observation period: 29FEB2024, 28FEB2025, 28FEB2026)

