#### 6.3.2.4. Discontinuation

Discontinuation will be defined as >67 days after last injection (monthly dosing) or >127 days after last injection (every other month dosing).

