#### 6.4. \*Data source

The OPERA® clinical cohort is a multi-site observational database built from the complete patient health records managed in EHR systems from more than 400 participating caregivers at 142 separate locations throughout the US (Figure 3). Through their membership in OPERA®, medical practices meet the Centers for Medicare & Medicaid Services (CMS) Merit-based Incentive Payment System (MIPS) Incentive Program for Integration with a Specialized Registry. OPERA®-participating physicians and ancillary healthcare providers have documented the care of over 1 million patients in their EHRs, including over 150,000 PWH of which approximately 20% are women, representing 13% of all the PWH linked to care in the US. The OPERA® database is refreshed from these EHR systems at each clinic daily providing up-to-date data for both clinicians and researchers. In total, there are more than 13 million documented prospective visits in the EHR systems for PWH and 4.5 million prescriptions written for ART medications. The average years of follow-up (years of documenting patient visits prospectively in the EHR) for PWH in OPERA® is 5.6 years and there are over 30,000 PWH who have ten years or more of follow-up.

Figure 1. United States Map of OPERA® HIV+ Population and Centers for

Disease Control (CDC) State-by-State Estimates (2017)

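### A first VL ≥200 still awaiting its confirming event at a data cut counts as no failure, which biases the CVF proportion downward

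*Protocol*

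**What the plan says.** Section 6.3.2.6 defines CVF among people suppressed at initiation as "2 consecutive follow-up VLs ≥200 copies/mL OR 1 follow-up VL ≥200 copies/mL + discontinuation within 4 months of VL ≥200 copies/mL". The definitions for people viremic at initiation likewise need a second high VL or a discontinuation. Section 6.3.2.4 sets when a stop becomes visible: "Discontinuation will be defined as >67 days after last injection (monthly dosing) or >127 days after last injection (every other month dosing".

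The censoring criteria in section 6.2 include "Study end (end of observation period: 29FEB2024, 28FEB2025, 28FEB2026". The eligibility and observation periods nearly coincide. For Year 3 they are "Period of eligibility: 21JAN2021-31DEC2023" and "Period of observation: 21JAN2021-29FEB2024", and Years 4 and 5 follow the same pattern ("Period of observation: 21JAN2021-28FEB2025" and "Period of observation: 21JAN2021-28FEB2026").

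CVF is summarised as a number and proportion of people, with time to failure (6.3.2.6). Its associated factors are studied by multiple logistic regression (6.7.1.1). Section 6.7.1.2 plans no sensitivity analysis. The Protocol gives no rule for a single VL ≥200 that is unresolved at the cut, and it does not fix whether failure is dated at the first VL or at confirmation.

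On timing, section 6.4 says "The OPERA® database is refreshed from these EHR systems at each clinic daily". The milestones put preliminary tables in May 2024, May 2025 and July 2026.

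**The concern.** Someone whose first VL ≥200 is drawn shortly before a cut, and whose repeat VL or stop falls after it, meets neither route of the definition on the data used. They enter the proportion as a non-failure and the logistic model as a zero. The error runs one way: the cut can remove would-be confirmed failures but cannot add any.

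CVF is part of virologic effectiveness (primary objective 3), is the outcome of primary objective 4, and decides who enters secondary objectives 5 and 6. A pending case is therefore also missing from the descriptions of resistance testing and of regimens after failure.

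**Working it through.** **1. The plan's own figures.** The Protocol gives no figure for CVF or for unconfirmed VLs. Its only checkable figures here are the precision values in Table 1. The Wald width 2 × 1.96 × √(p(1−p)/n) at p = 0.5 gives 0.046, 0.049, 0.168 and 0.203 for n = 1843, 1578, 136 and 93. These agree with the stated 0.05, 0.05, 0.17 and 0.20.

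**2. Dates (section 6.2).** Counting from 21JAN2021, eligibility ends at day E and observation at day O:
- Year 3: E = 1,074, O = 1,134, a run-out of 60 days
- Year 4: E = 1,440, O = 1,499, a run-out of 59 days
- Year 5: E = 1,805, O = 1,864, a run-out of 59 days

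The run-out is shorter than 4 months (about 122 days) and shorter than both the 67-day and the 127-day threshold. For example, a person on every-other-month dosing last injected on 25OCT2023 is exactly 127 days out on 29FEB2024, so is not yet a discontinuer.

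**3. Share of at-risk time near the cut.** Assume a low constant failure hazard and uniform entry. If every repeat came exactly W days after the first VL, the share lost equals the share of at-risk time in the last W days. With no stopping:

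share = [(O−W)·W + (W² − (O−E)²)/2] / [(O² − (O−E)²)/2]

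With W = 122:
- Year 3: (123,464 + 5,642) / 641,178 = 20.1%
- Year 4: (167,994 + 5,701.5) / 1,121,760 = 15.5%
- Year 5: (212,524 + 5,701.5) / 1,735,507.5 = 12.6%

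Weighting each day by survival on regimen at 15% stopping per year brings these to 18.8%, 14.2% and 11.3%.

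**4. Variable retest time.** Repeats do not all arrive at a fixed interval. Taking the wait as exponential with a given mean, and keeping 15% stopping per year, the share of would-be CVFs still unconfirmed at the cut is:

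| Retest assumption | Entry | Year 3 | Year 4 | Year 5 |
|---|---|---|---|---|
| mean 30 days | uniform | 4.7% | 3.4% | 2.7% |
| mean 60 days | uniform | 9.3% | 6.8% | 5.3% |
| mean 120 days | uniform | 17.6% | 13.3% | 10.7% |
| mean 120 days | rising linearly | 24.4% | 19.3% | 15.9% |
| fixed 6 months | rising linearly | 39% | 31% | 25% |

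Only VLs that would eventually be confirmed are counted. Those that would re-suppress are not in the numerator.

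**5. Absolute size.** The Protocol gives no CVF proportion, so two are assumed, with n = 1,578.
- At a true 1%, a loss of 5–25% is 0.05–0.25 percentage points, against a Wald half-width of 0.49.
- At a true 5%, the same loss is 0.25–1.25 points, against 1.08.

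**6. What a later look recovers at Year 5.** From 28FEB2026 to 1 July 2026 is 123 days. With an exponential wait of mean m, the fraction of pending cases resolved is 1 − exp(−123/m): 98% for m = 30, 87% for m = 60 and 64% for m = 120. With a fixed 122-day interval all are resolved. With a fixed 6 months (183 days) it is about 123/183 = 67%.

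**The case against.** The strongest objection is that classifying a pending VL at a data cut, and choosing the extraction date, is detail for an SAP that is not shown. The definition itself is not wrong, and no sentence says outright that a pending VL is a non-failure. That is fair as far as it goes, and an SAP could already deal with it. But the Protocol itself fixes the definition, the censoring date, the yes/no measure, the logistic model and the absence of sensitivity analyses, and together these produce the result.

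A second objection is that if failure is dated at confirmation, a confirmation after the cut is ordinary right-censoring. That is sound for a rate based on person-time. It does not help a simple proportion or a logistic model, neither of which uses person-time.

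A third is that the loss is small and partly corrects itself. Much of this stands. At an assumed CVF of 1% the loss is below sampling error. Every analysis restarts from 21JAN2021, so a case pending at Year 3 or 4 can be picked up later. The bias does not shrink as the cohort grows, however, and Year 5 has no later cut.

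A reader might also infer stronger claims that the documents do not support:
- **That a late VL has no time to be confirmed.** A repeat can be drawn within weeks, and a person already late for an injection can pass the threshold before the cut.
- **That Year 3 must be worst.** This holds in relative terms for steady, falling or smoothly rising entry. It fails if entry jumps. With entry tripled from 2024, the 122-day shares are 18.8%, 19.2% and 15.8%.
- **That the oral-versus-injectable comparison is distorted.** Nothing in the Protocol says that VL testing intervals differ between the groups, or in which direction.
- **That the odds ratios for objective 4 are materially biased.** Non-differential loss of a rare outcome's cases leaves them almost unchanged, and no differential loss by any listed factor has been shown.

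**Conclusion.** The point holds in a limited form. The mechanism and its downward direction follow from the text. The size does not, because it rests on assumed retest interval, accrual and stopping rate. With uniform entry and 15% stopping per year, the loss at Year 5, the cut that stays uncorrected, is about 3–11% of would-be CVFs for retest intervals from a 30-day mean to about 4 months. Rising entry or less frequent testing takes it higher. This is a modest, one-directional and avoidable bias in a primary outcome. It is worth correcting but does not by itself undermine the study.

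**What to change.** State that failure is dated at the first VL ≥200 and that this VL must fall on or before the cut. Read the confirming VL or discontinuation from records up to a fixed extraction date after the cut, named in advance for each analysis. For Year 5, the gap between 28FEB2026 and the July 2026 preliminary tables already allows this. For earlier cuts, use whatever run-out the table schedule permits; preliminary tables in May leave at least 62 days from the end of February to 1 May.

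At each cut, report the number of single VLs ≥200 still unresolved at extraction, and show the CVF proportion a second time with all of them counted as failures. This is an upper bound, since some will have re-suppressed.

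The cost is a later extraction date for one variable, one extra table row and a short wording change. No new data collection is needed. Ending CVF follow-up some months before the cut is not recommended, because it discards at-risk time and drops the most recent starters.

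### The single-viral-load limb of confirmed virologic failure has a window shorter than the lag that defines discontinuation, the discontinuation date is not stated, and the failure rule differs between strata that are compared

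*Protocol*

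**What the plan says.** Discontinuation (protocol 6.3.2.4) is defined by elapsed time alone: "Discontinuation will be defined as >67 days after last injection (monthly dosing) or >127 days after last injection (every other month dosing". Neither that section nor 6.3.2.3 (Persistence) says whether the date assigned is the last injection, the day the threshold is crossed, or another day. Section 6.2 lists discontinuation as a censoring event.

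Section 6.3.2.6 gives two CVF rules.

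- **Suppressed at initiation (VL below 50).** Two high VLs in a row, each 200 or more, are enough. A lone high value also suffices under the alternative limb, which is worded "1 follow-up VL ≥200 copies/mL + discontinuation within 4 months of VL ≥200 copies/mL". The four months apply whatever the dosing schedule.
- **Viremic at initiation (VL 50 or more).** After suppression to below 50, either two VLs of 200 or more, not stated to be consecutive, or a lone VL of that size with a window that depends on dosing: four months for people injected every other month, whereas the version for monthly users is "discontinuation within 2 months for monthly regimen". The same structure is repeated at a threshold of 400.

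Section 6.3.3.2 says that virologic effectiveness will be compared between these two VL strata.

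**The concern.** The single-VL limb is there for the person whose VL is high and who then receives no further injection, so that no second VL on regimen is available. The most direct example is a high VL drawn at the last injection visit. By the protocol's own definition, discontinuation cannot be established until a little over four months (or two months) after that visit, yet the limb requires it within four (or two) months of the VL.

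CVF is part of primary objective 3 and is the outcome of primary objective 4. It is compared with oral ART under secondary objective 3 and defines the cohorts for secondary objectives 5 and 6. The resistance-testing window in 6.3.2.7 is also counted from it. Section 6.7.1.2 plans no sensitivity analysis that would show how far CVF depends on the reading chosen.

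**Working it through.** **Inputs.**
- Lag before discontinuation (6.3.2.4): more than 127 days, so day 128 at the earliest, for every other month dosing; more than 67 days, so day 68, for monthly dosing.
- Single-VL window (6.3.2.6): four months for all suppressed starters and for viremic starters on every other month dosing; two months for viremic starters on monthly dosing.
- Days per month: the protocol gives no conversion. Assumption: calendar months, so four months are 120-123 days and two months are 59-62 days, depending on the start date.

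**Reading A: discontinuation is dated when the threshold is crossed.** Shortfall for a VL drawn on the day of the last injection = first possible discontinuation day minus window.

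| Group | Window (days) | First discontinuation day | Shortfall (days) |
|---|---|---|---|
| Every other month, both strata | 120-123 | 128 | 128 - 123 = 5 to 128 - 120 = 8 |
| Monthly, viremic | 59-62 | 68 | 68 - 62 = 6 to 68 - 59 = 9 |
| Monthly, suppressed | 120-123 | 68 | none: 120 - 68 = 52 to 123 - 68 = 55 to spare |

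Fixed month lengths do not change the result. At 31 days per month the shortfall is 128 - 124 = 4 and 68 - 62 = 6 days. At 28 days it is 128 - 112 = 16 and 68 - 56 = 12 days. In the first two rows the last-visit VL fails this limb under every conversion. With calendar months, the earliest VL that qualifies is drawn on day 5-8 (every other month) or day 6-9 (monthly, viremic) after the last injection.

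**Reading B: discontinuation is dated at the last injection.** The lag from a last-visit VL is 0 days, so that VL counts in every group. But follow-up is censored at discontinuation, so a VL drawn after the last injection is no longer a follow-up VL.

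**The two readings together.** In the first two rows, reading A accepts single VLs only from about day 5-9 after the last injection onward, and reading B accepts them only up to day 0. The two sets do not overlap. A VL drawn in the first few days after the last injection (days 1-4 for every other month, days 1-5 for monthly viremic) counts under neither.

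**Difference between strata, whichever date is used.**
- *Two-VL limb.* Take a person who has reached VL below 50 and then has 200 or more, below 50, and 200 or more again. Read literally, the viremic rule counts this as CVF; the suppressed rule does not, because the high values are not consecutive.
- *Single-VL limb.* Take a monthly user with a high VL at the last injection visit, under reading A. A suppressed starter counts (68 is within 120-123). A viremic starter who had since suppressed does not (68 exceeds 59-62).

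The first difference makes the viremic rule wider and the second makes it narrower, so the net direction is not determined.

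**The case against.** The strongest reply is that assigning an event date is commonly left to the statistical analysis plan, which is not shown, and that dating discontinuation at the last injection makes the last-visit VL count everywhere. That stands as far as it goes: the shortfall depends on the date. It does not settle the matter, because that dating combined with the protocol's censoring rule loses later VLs instead. The window lengths and the thresholds that do not fit them are fixed in the protocol itself.

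A second reply is that the viremic rule was added on purpose. The Amendment 2 summary of changes ties it to HHS guidelines, the sponsor's observational definitions and FDA's proposed assessments. That supports the prior-suppression condition and the 400 threshold. It does not explain why suppressed starters on monthly dosing keep a four-month window, or why the word consecutive appears in one stratum only.

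A reader might also infer more than the protocol supports:

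- *That a high VL at the last visit can never count as CVF.* It can, through the two-VL limb, if an adjacent follow-up VL is also 200 or more.
- *That the two-month mismatch is general.* It concerns monthly users in the viremic stratum only; that stratum was 229 of 1,843 people in the two-year count (section 6.5), with no split by dosing.
- *That a large share of failures is missed.* Any percentage would need the share of CVFs resting on one VL and the share of VLs drawn at injection visits. The protocol gives neither.
- *That comparisons between dosing schedules are biased.* None is planned: dosing is described as a pattern of use, and it is neither a stratum nor a named regression factor in 6.7.1.1.

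**Conclusion.** The point holds in a limited form. Sections 6.3.2.4 and 6.3.2.6 do not fit together. If discontinuation is dated at threshold crossing, the single-VL window is 5-8 days too short for every other month dosing in both strata and 6-9 days too short for monthly dosing in the viremic stratum, assuming calendar months. If it is dated at the last injection, the limb selects a different set of people. Separately, the two strata have different CVF rules although they are to be compared, so part of any difference in CVF between them may come from the definition. The number of people misclassified cannot be computed from the protocol. Because CVF is a primary outcome and the correction is one of wording, it should be made before the Year 5 analysis, planned for 3Q2026.

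**What to change.** Reconcile the censoring criteria in 6.2 with 6.3.2.4 and 6.3.2.6. These are outcome definitions; nothing here concerns how patients are managed.

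1. State the calendar date of discontinuation, and use it consistently for CVF and for censoring.
2. Set the single-VL window in line with the 127/67-day thresholds, so that a qualifying VL drawn at or after the last injection counts. With threshold dating, the window must reach at least 128 days (every other month) or 68 days (monthly) from the VL. With last-injection dating, VLs drawn between the last injection and the threshold must be explicitly admitted.
3. Apply the same dosing-specific window and the same consecutive-VL requirement in both strata. Keep the prior-suppression condition and the additional 400-copies version for viremic starters.

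The cost is re-running the CVF algorithm on existing data, including Year 3, whose final tables were planned for August 2024, so that the years remain comparable. Counts need not move in one direction only: for suppressed starters on monthly dosing, a common dosing-specific window would be shorter than the present 120-123 days, and requiring consecutive VLs would narrow the viremic rule.
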